Appendix VIII – Uniscale

Appendix IX – Was It Worth It

Appendix X – Child-Pugh Classification

Appendix XI: MEDICATION GUIDE Iclusig[®] (eye-CLUE-sig) (ponatinib) Tablets

Appendix XII: Prohibited Drugs Affecting the QT Interval

Schema

If a patient is deemed ineligible or a cancel, please refer to Section 13.0 for follow-up information.

* Cycle = 28days

Generic name: Ponatinib
Brand name(s): Iclusig™
Mayo Abbreviation: PONATINIB
Availability: provided by ARIAD Pharmaceuticals

1.0 Background

1.1 Biliary Cancers

Biliary cancers comprise malignant tumors of the intrahepatic and extrahepatic bile ducts, gallbladder and ampulla. Known risk factors for cholangiocarcinoma are the liver flukes *O. viverrini* and *C. sinensis* in high prevalence endemic regions in southeast Asia,¹⁻³ as well as primary sclerosing cholangitis,⁴⁻⁷ Caroli's disease,⁸ hepatitis B and hepatitis C,⁹⁻¹⁴ obesity,¹³ hepatolithiasis^{15, 16} and thorotrast contrast exposure.^{17, 18} Increased incidence of gallbladder cancer has been associated with gallstones, obesity, age, female gender, and *S. typhi*, *S. paratyphi*, *H. pylori* and *H. bilis* infections.¹⁹ Regions of higher incidence include Chile²⁰ and Northern India/Pakistan.¹⁹

Surgical approaches such as resection and transplantation represent the only curative treatment approaches.²¹ Unfortunately, most patients present with surgically unresectable or metastatic disease at diagnosis. Systemic therapy with gemcitabine and cisplatin has been established as the standard of care for patients with advanced disease.²² However, most patients eventually experience progression of their disease and there is imminent need for novel therapeutic approaches.

1.2 FGFR Pathway in Cancer

Members of the FGFR family (FGFR1-4) have been associated with mutations, amplifications and translocation events with oncogenic potential.²³ FGFR fusions with oncogenic activity have been previously identified in bladder cancer (FGFR3),²⁴ lymphoma (FGFR1 and FGFR3),^{25, 26} acute myeloid leukemia (FGFR1),²⁷ multiple myeloma,²⁸ myeloproliferative neoplasms²⁹ and most recently glioblastoma multiforme (FGFR1 and FGFR3).³⁰ Fusions involving FGFR family members may be both therapeutically relevant and actionable. The FGFR tyrosine kinase inhibitors (TKI) dovitinib³¹ and NVP-BGJ398³² are currently in clinical development and the FGFR TKI ponatinib³³ was recently approved by the FDA for use in T315I mutant chronic myelogenous leukemia. FGF7 (keratinocyte growth factor) has been previously linked to poor prognosis in patients with biliary tract cancer and a small molecule FGFR kinase inhibitor, Ki23057, has demonstrated efficacy in preclinical models.³⁴ FGFR2, FGFR3 and FGFR4 have been found to be overexpressed in biliary cancers, particularly those harboring IDH1 and 2 mutations.³⁵

We have identified recurrent fusions of FGFR2 in patients with advanced intrahepatic cholangiocarcinoma in the setting of ongoing whole genome sequencing studies. Concomitant activation of the FGFR cascade (phosphor-FGFR2, increased expression of other FGFR members: FGFR3 and FGFR4) has been elucidated in these instances. We found fusions of FGFR2 with MGEA5, BICC1 or TACC3 in our study. The FGFR genes encode multiple structural variants through alternative splicing. Notably, the FGFR2-IIIb isoform was present in all of these fusions and has been shown to have selectivity for epithelial cells as opposed to the FGFR2-IIIc isoform, which is found selectively in mesenchymal cells.³⁶ Given that biliary cancers are of epithelial origin and that cancer associated fibroblasts have been implicated in the setting of a paracrine loop with cholangiocarcinoma tumor cells,^{37, 38} further characterization of FGFR2-IIIb specific ligands, FGF7 and FGF10, which have no binding to FGFR2-IIIc, would be warranted. Paradoxically, FGFR2-IIIb has been described as a tumor suppressor in pre-clinical systems of bladder cancer and prostate cancer.^{39, 40} As such, FGFR signaling is clearly context dependent and will exhibit variability in disparate tumor types.

Additional studies to characterize the prevalence of the recently identified FGFR2 aberrations in a larger cohort of biliary cancers are underway. *In vitro* functional studies characterizing the fusions are also underway.

We propose to study ponatinib prospectively in the context of a pilot study in patients with FGFR2 fusions that are identified through our real time whole genome analysis efforts.

1.2 Ponatinib

1.21 Chemical

AP24534 (United States Adopted Name [USAN]: ponatinib) is a novel, orally-available tyrosine kinase inhibitor (TKI). A primary target is BCR-ABL, an abnormal tyrosine kinase that is the hallmark of chronic myeloid leukemia (CML). BCR-ABL is expressed from a fusion gene formed by the rearrangement of the breakpoint cluster region (BCR) on chromosome 22 with the c-abl proto-oncogene (ABL) on chromosome 9 (BCR-ABL). Ponatinib is a new chemical entity prepared by chemical synthesis. The ponatinib active pharmaceutical ingredient (API) is the mono-hydrochloride salt (AP24534 hydrochloride, or AP24534 HCl). Ponatinib for investigational use is supplied as white opaque capsules containing nominally 2 mg, 5 mg or 15 mg of ponatinib or as 15 mg or 45 mg round, white, film-coated tablets.

1.22 Nonclinical

A preclinical development program has been completed to support clinical trials on ponatinib. *In vitro* assays demonstrated that ponatinib potently inhibits the kinase enzymatic activity of the T315I ABL kinase domain, as well as that of the native (unmutated) enzyme. In leukemia cell lines expressing these BCR-ABL variants, ponatinib potently inhibited BCR-ABL signaling, leading to inhibition of cellular proliferation and induction of apoptosis. Ponatinib also potently inhibits the proliferation of cell lines expressing other major clinically observed imatinib-resistant mutants of BCR-ABL. *In vivo* antitumor activity has been shown in tumor-bearing mouse models.

Ponatinib is also a potent inhibitor of certain other tyrosine kinases implicated in the initiation and progression of leukemias and other tumor types. In particular, it inhibits FLT3, which is frequently mutationally activated in acute myeloid leukemia (AML), and inhibits all members of the FGFR family, which are implicated in a variety of myeloproliferative disorders and solid tumor indications. Ponatinib also inhibits several other kinases, including KIT, RET, SRC, VEGFR, PDGFR, and TIE2. Taken together, the kinase inhibition profile of ponatinib suggests the potential for clinical activity in other hematologic and nonhematologic malignancies in addition to CML.

Preclinical safety assessment studies were performed on ponatinib including 6-month oral toxicology studies in rats and cynomolgus monkeys. The rat was shown to be the most sensitive species to the toxicologic effects of ponatinib. In the 6-month oral toxicology study in rats, the no observed adverse effect level (NOAEL) was 0.25 mg/kg/day. Higher dose levels of 0.75 and 2 mg/kg/day caused mortality of some animals. Histologic examination revealed decreased

numbers of chondrocytes along the physis in the femur at the 0.75 and 2 mg/kg/day dose levels, and lymphoid depletion was observed in the thymus at the 2 mg/kg/day dose level. The administration of ponatinib to cynomolgus monkeys for 6 months at oral dose levels of 0.25, 0.75 and 2 mg/kg/day was well tolerated with no ponatinib-related microscopic findings being observed at any dose level. Toxicity studies in pregnant rats demonstrated fetal malformations and embryo-fetal toxicity at dose levels of 1 and 3 mg/kg/day, respectively, and higher. In a phototoxicity study in pigmented rats, signs of minimal ocular phototoxicity were observed at 5 and 10 mg/kg.

1.23 Clinical

Iclusig received accelerated approval in the United States (US) (December 2012) and approval in the European Union (EU) (July 2013) for patients with refractory CML or Philadelphia chromosome-positive (Ph+) leukemias. As of 06 January 2014, 753 patients have received ponatinib therapy through clinical studies, and 1312 through global expanded access programs.

Following approval of ponatinib in the US and the EU, more than 900 patients have been treated with ponatinib commercially. Since the previous update to this Investigator Brochure (Version 5, 25 February 2013), regulatory actions were taken by ARIAD Pharmaceuticals (ARIAD) and/or the competent authorities following increased cumulative risk of vascular occlusive events observed in patients using ponatinib. From a development perspective, on 08 October 2013, the US Food and Drug Administration (FDA) placed a partial clinical hold on all new patient enrollments in clinical studies with ponatinib, and a phase 3 study (EPIC: AP24534-12-301) was terminated on 17 October 2013. From a postmarketing authorization perspective, prior approval supplement/type II variation were evaluated by the FDA and the European Medicines Agency (EMA), respectively, to revise ponatinib product information to include updated data and warning/precautions on arterial thromboembolic events, venous thromboembolic events, cardiac failure/left ventricular dysfunction (LVD), and cardiovascular deaths. The type II variation received a positive opinion from Europe's Committee for Human Medicinal Products (CHMP) on 21 November 2013. Subsequent to completion of the Type II variation procedure, a referral procedure under article 20 of regulation (EC) No. 726/2004 was triggered. In the US, while evaluation of new safety data was ongoing, the FDA requested ARIAD on 31 October 2013 to temporarily suspend commercial distribution and marketing of Iclusig in the US. On 20 December 2013, the FDA agreed with the revised US Prescribing Information, and commercialization of Iclusig was resumed in the US in January 2014. Additional information can be found within the Investigator's brochure.

1.3 Circulating tumor DNA based biomarkers

Cell-free tumor-specific DNA in circulating plasma (ctDNA) has been recently shown to be a potential biomarker for solid cancers. Specific mutations can be tracked in ctDNA and reflect disease burden in breast, ovarian, colorectal and other non-hematological cancers. Extensive analysis of selected plasma samples can provide insights into acquired resistance to molecularly targeted treatments and sub-clonal genomic evolution of cancers.

There is a dire need for accurate circulating biomarkers for cholangiocarcinomas. Analysis of ctDNA within this study provides an opportunity to develop a personalized biomarker for monitoring of tumor burden. Additional correlative analysis may allow identification of mechanisms that cause primary or acquired resistance to treatment ponatinib in cholangiocarcinoma. This may enable molecular stratification of cholangiocarcinoma for ponatinib or other molecularly targeted agents using circulating tumor DNA analysis.

2.0 Goals

2.1 Primary

2.11 To assess the clinical benefit rate (confirmed complete or partial response or stable disease for 4 or more cycles) of ponatinib in FGFR aberrant advanced biliary cancers

2.2 Secondary

2.21 To estimate progression free survival, overall survival, and CA19-9 response rate of these patients

2.22 To estimate the adverse event profile of ponatinib

2.3 Translational/Correlative Research

2.31 Establish preliminary correlations between FGFR2 fusions and evidence of any clinical benefit

2.32 Assess preliminary evaluation of FGFR2 pathway perturbation with ponatinib

2.33 To describe patient-reported health-related quality of life and symptoms

3.0 Patient Eligibility

3.1 Inclusion Criteria

3.11 Age \geq 18 years

3.12 Histological/cytological confirmation of biliary cancer.

3.13 Confirmation of advanced biliary cancer that is refractory or intolerant to gemcitabine or fluoropyrimidine based therapy with FGFR2 fusion [using Next-Gen sequencing assays (such as Foundation One®) or fluorescent in situ hybridization (FISH) break-apart assays] or FGFR pathway mutation/amplification [using Next-Gen sequencing assays (such as Foundation One®)]. Assays must be performed in a CLIA certified laboratory and done as a CLIA validated test or RUO in a CLIA laboratory.

3.14 Measurable disease as defined in Section 11.0.

3.15 ECOG Performance Status (PS) 0, 1 or 2 (Appendix I).

- 3.16 The following laboratory values obtained ≤ 14 days prior to registration.
- Absolute neutrophil count (ANC) $\geq 1500/\text{mm}^3$
 - Platelet count $\geq 100,000/\text{mm}^3$
 - Hemoglobin ≥ 9.0 g/dL
 - Total bilirubin ≤ 1.5 x upper limit of normal (ULN), unless due to Gilbert's syndrome
 - Aspartate transaminase (AST) and Alanine Aminotransferase (ALT) < 3 x ULN
 - Creatinine ≤ 1.5 x upper limit of normal (ULN)
 - Serum lipase and amylase ≤ 2.5 x upper limit of normal (ULN). Note: If subject has tumor involvement in the liver ≤ 3 x ULN.
- 3.17 Negative pregnancy test done ≤ 7 days prior to registration, for women of childbearing potential only.
- 3.18 Recovered from prior radiotherapy and/or systemic therapy related toxicities to Grade ≤ 1
- 3.19a Provide informed written consent.
- 3.19b Life expectancy ≥ 3 months
- 3.19c Willing to return to enrolling institution for follow-up (during the Active Monitoring Phase of the study).
- Note: During the **Active Monitoring** Phase of a study (i.e., active treatment and observation), participants must be willing to return to the consenting institution for follow-up.*
- 3.19d Female and male patients who are fertile agree to use an effective form of contraception with their sexual partners from registration through 4 months after the end of treatment.
- 3.19e Ability to complete questionnaire(s) by themselves or with assistance.

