3.2 Exclusion Criteria

- 3.21 Any of the following because this study involves an investigational agent whose genotoxic, mutagenic and teratogenic effects on the developing fetus and newborn are unknown:
- Pregnant women
 - Nursing women
 - Men or women of childbearing potential who are unwilling to employ adequate contraception
- 3.22 Co-morbid systemic illnesses or other severe concurrent disease which, in the judgment of the investigator, would make the patient inappropriate for entry into

this study or interfere significantly with the proper assessment of safety and toxicity of the prescribed regimens.

- 3.23 Immunocompromised patients and patients known to be HIV positive and currently receiving antiretroviral therapy. NOTE: Patients with a known history of HIV infection are not eligible for this trial.
- 3.24 Uncontrolled intercurrent illness including, but not limited to, ongoing or active infection, symptomatic congestive heart failure, unstable angina pectoris, cardiac arrhythmia, or psychiatric illness/social situations that would limit compliance with study requirements.
- 3.25 Receiving any other investigational agent which would be considered as a treatment for the primary neoplasm.
- 3.26 Prior systemic chemotherapy, radiation therapy or major surgery \leq 30 days prior to registration.
- 3.27 Concurrent use of any other approved or investigational anticancer agents, including hormonal agents
- 3.28 Prior nitrosourea or mitomycin C \leq 6 weeks prior to registration.
- 3.29a Patients with gastrointestinal comorbidities that would affect intake or absorption of ponatinib
- 3.29b Untreated or progressive brain metastases
- 3.29c Prior treatment with or allergic reactions attributed to compounds of similar chemical or biologic composition to ponatinib
- 3.29d Clinically uncontrolled hypertension (diastolic blood pressure >90 mm Hg; systolic >140 mm Hg). NOTE: Patients with hypertension should be undergoing treatment at study entry for blood pressure control.
- 3.29e Previous or concurrent malignancy except adequately treated basal or squamous cell skin cancer, in situ carcinoma of the cervix, or other solid tumor treated curatively and without evidence of recurrence for at least 5 years
- 3.29f History of significant bleeding disorder unrelated to cancer
- 3.29g History of acute pancreatitis within 1 year prior to registration, chronic pancreatitis, alcohol abuse or uncontrolled hypertriglyceridemia (triglycerides >450 mg/dL)

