4.0 Test Schedule

Cycle = 28 days

Tests and procedures	Active Monitoring Phase						
	≤14 days prior to registration	Cycle 1 Day 1 (± 2 days) prior to treatment	Cycle 1 Days 8, 15, 22 prior to treatment	Cycle 2 and beyond Day 1 (± 2 days) prior to treatment	Q 8 weeks from Cycle 1 Day 1 (± 5 days)	Every 3 Cycles starting at end of Cycle 3 (± 5 days)	End of treatment
History and exam, wt, ECOG	X			X			X
Height, Child Pugh score	X						
Vitals ³	X	X	X	X			X
Hematology group WBC, ANC, Hgb, PLT	X	X	X	X			X
Chemistry group Sodium, potassium, chloride, bicarbonate, total protein, albumin, calcium, glucose, BUN, total bilirubin, creatinine, alkaline phosphatase, SGOT (AST), SGPT (ALT)	X	X		X			X
Amylase ^R	X	X	X	X			
Lipase ^R	X	X	X	X			
CA19-9		X		X ⁵			
EKG ^R	X					X	
Echocardiogram	X			X ¹⁰			
Tumor measurement and Imaging (CT or MRI as clinically)	X ¹				X ²		

indicated)							
Pregnancy test	X ⁴						
Patient questionnaire booklet	X ⁹			X ⁹			
Adverse event assessment	X		X	X			
Research Archival Tissue (optional)	X ⁸						
Research Tissue Biopsy (optional)				X ^{7,R}			X ⁶
Research blood samples (Optional)	X			X			X

1. Imaging studies such as CT scans, and MRIs can be performed ≤ 28 days prior to registration. Use same imaging throughout the study. Assessment by physical exam should be done ≤ 14 days prior to registration.
 2. Tumor assessment must be performed at least every 8 weeks. Tumor assessment should be performed at any time during the treatment cycle that disease progression is clinically suspected so that patient can go off treatment and receive other therapy.
 3. Includes weight, blood pressure, pulse and temperature
 4. Women of childbearing potential only. Must be done ≤ 7 days prior to registration.
 5. Only to be collected if $> \text{ULN}$ on Cycle 1 Day 1
 6. If patient has experienced disease progression and at such time a standard of care biopsy is ordered by the treating physician, waste specimen will be collected, fresh frozen and stored for future correlative studies. Perform only if archival specimen was available.
 7. Perform only if archival specimen was available.
 8. Archival FFPE and/or fresh frozen tissue collected in setting of standard of care procedures.
 9. Patient questionnaire booklet must be used; copies are not acceptable for this submission. Booklet should be completed by patient prior to review of treatment response and discussions of patient's general health since last treatment evaluation.

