6.4 An optional correlative research component is part of this study, there will be an option to select if the patient is to be registered onto this component (see Sections 14.0 and 17.0).

- Patient has/has not given permission to have a tissue biopsy at cycle 2, day 1.
 - Patient has/has not given permission to allow any excess tissue collected while on this study to be used for research studies
 - Patient has/has not given permission for blood collection at screening, Prior to each cycle, and at end of study to be used for research studies.
- 6.5 At the time of registration, the following will be recorded:
- Patient has/has not given permission for his/her tissue and blood sample(s) to be stored and used in future research of biliary cancer at Mayo Clinic
 - Patient has/has not given permission for his/her tissue and blood sample(s) to be stored and used in future research at Mayo Clinic to learn about, prevent, or treat any other health problems
 - Patient has/has not given permission for Mayo Clinic to give his/her tissue and blood sample(s) to researchers at other institutions
- 6.6 Treatment cannot begin prior to registration and must begin ≤ 7 days after registration.
- 6.7 Pretreatment tests/procedures (see Section 4.0) must be completed within the guidelines specified on the test schedule.
- 6.8 All required baseline symptoms (see Section 10.6) must be documented and graded.
- 6.9a Treatment on this protocol must commence at a Mayo Clinic institution under the supervision of a medical oncologist.
- 6.9b Study drug is available on site.
- 6.9c Patient questionnaire booklet is available on site; copies are not acceptable for this submission.

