16.2 Statistical Design

16.21 The largest clinical benefit where the proposed treatment regimen would be considered ineffective in this population is 5%, and the smallest clinical benefit rate that would warrant subsequent studies with the proposed regimen in this patient population is 20%. The following two-stage Simon Optimum design uses 10 or 27 patients to test the null hypothesis that the true clinical benefit rate in a given patient population is at most 5%.

The null clinical benefit rate of 5% is based on response rates observed for refractory solid tumors with single agents in an unselected/empiric setting (Horstmann, E. et al., 2005).

16.211 STAGE 1: Enter 10 patients into the study. If 0 successes (i.e., patients deemed as having clinical benefit) are observed in the first 10 evaluable patients, we will consider this regimen ineffective in this patient population and terminate this study. Otherwise, if the number of successes is at least 1, we will proceed to Stage 2.

16.212 STAGE 2: Enter an additional 17 patients into the study. If 2 or fewer successes are observed in the first 27 evaluable patients, we will consider this regimen ineffective in this patient population. If 3 or more successes are observed in the first 27 evaluable patients, we may recommend further testing of this regimen in subsequent studies in this population.

16.213 NOTE: Accrual will be suspended between stages to allow patients to become evaluable for the primary endpoint.

16.211 Over Accrual: If more than the target number of patients are accrued, the additional patients will not be used to evaluate the stopping rule or used in any decision making process. Analysis involving over accrued patients is discussed in Section 16.313.

16.22 Sample Size: The two-stage study design to be utilized is fully described in Section 16.21. A minimum of 10 and a maximum of 27 evaluable patients accrued onto this study unless undue adverse events are encountered. We anticipate accruing an additional 3 patients to account for ineligibility, cancellation, major treatment violation, or other reasons. Thus, **a maximum of 30 patients will be accrued onto this study** in order to have 27 evaluable patients available for the statistical design described in Section 16.21.

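### Patients not progressing at entry are eligible and not identified, yet lasting stable disease counts as success against a null from refractory tumors; among systemic drugs, only chemotherapy has a stated washout.

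*Combined protocol and SAP*

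**What the plan says.** **Entry.** Section 3.13 requires disease that is "refractory or intolerant to gemcitabine or fluoropyrimidine based therapy with FGFR2 fusion" or another FGFR pathway alteration. Intolerance alone is enough. Nothing in 3.1 or 3.2 asks for progression before registration. Section 5.0 sets no stratification factor, and the descriptive factors in Section 12 include neither progression at entry nor the reason the last therapy ended.

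**Washout.** Section 3.26 sets 30 days before registration for "Prior systemic chemotherapy, radiation therapy or major surgery". Section 3.28 sets 6 weeks for "Prior nitrosourea or mitomycin C". Two further exclusions cover ongoing use only: 3.25 ("Receiving any other investigational agent which would be considered as a treatment for the primary neoplasm") and 3.27 ("Concurrent use of any other approved or investigational anticancer agents, including hormonal agents"). Section 3.18 refers to systemic therapy in general, but asks only that toxicity has settled to Grade 1 or less. Section 3.29c bars earlier treatment with compounds similar to ponatinib, with no time limit.

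**Timing.** Footnote 1 of the Section 4.0 test schedule reads "Imaging studies such as CT scans, and MRIs can be performed ≤ 28 days prior to registration". Section 6.6 adds: "Treatment cannot begin prior to registration and must begin ≤ 7 days after registration".

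**Endpoint and null.** Section 16.11 counts a confirmed CR or PR, or SD for 4 or more cycles, as clinical benefit. Section 16.21 sets the null at 5%, taken from "response rates observed for refractory solid tumors with single agents in an unselected/empiric setting". The trial stops at 0 of 10 and is positive at 3 or more of 27.

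**The concern.** In a single-arm trial, stable disease points to drug activity only if the disease would otherwise have progressed. For a patient who left chemotherapy because of toxicity while the tumor was controlled, four stable cycles may simply continue the state at entry. The null describes refractory disease, so the enrolled population is wider than the one behind it, and wider in the direction that makes lasting SD easier to reach. Three successes in 27 are enough for a positive result, so a few such patients matter. Because entry status is not among the recorded factors, the final report could not separate them.

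The washout gap is a second, smaller route. A targeted, biologic or investigational agent that 3.29c does not bar could be stopped the day before registration without breaching any stated interval.

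**Working it through.** **Inputs.** Stage 1: n=10, stop at 0 successes. Stage 2: 17 more, positive at 3 or more of 27. Null 5%, alternative 20% (16.21). Stated significance level below 0.15 (16.24).

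**Formula.** With X ~ Bin(10, p) and Y ~ Bin(17, p), the probability of a positive result is

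P(go) = 1 − P(X=0) − P(X=1)·P(Y≤1) − P(X=2)·P(Y=0).

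**The plan's own figure.** At p=0.05: P(X=0)=0.5987; P(X=1)·P(Y≤1)=0.3151×0.7922=0.2496; P(X=2)·P(Y=0)=0.0746×0.4181=0.0312. P(go)=0.1204, against 0.12 in the table. At p=0.20 it is 0.8541, against 0.85. The rates 0.10, 0.15 and 0.25 also reproduce (0.4324, 0.6980, 0.9322). The arithmetic in 16.24 is correct; the question is whether 5% describes the admitted patients.

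**Effect of non-progressing patients when the drug is inactive.** Let f be their share and s their rate of SD for 4 or more cycles without any ponatinib effect. Give all other patients the plan's 5%. The pooled rate is p = (1−f)×0.05 + f×s. The documents give neither f nor s, so both are assumptions, as is 5% for the refractory group.

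| f | s | pooled p | P(go) |
|---|---|---|---|
| any | 5% | 0.050 | 0.120 |
| 10% | 10% | 0.055 | 0.148 |
| 10% | 20% | 0.065 | 0.207 |
| 20% | 10% | 0.060 | 0.177 |
| 20% | 20% | 0.080 | 0.303 |
| 20% | 30% | 0.100 | 0.432 |
| 30% | 30% | 0.125 | 0.579 |

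**Where the limit is passed.** P(go) is 0.148 at a pooled rate of 5.5% and 0.153 at 5.6%. Since p − 0.05 = f×(s−0.05), the limit is passed once f×(s−0.05) is slightly above 0.005. That means s just above 10% when f=10% (0.005/0.10 = 0.05 above the null), or just above 7.5% when f=20% (0.005/0.20 = 0.025 above the null).

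**Timing.** A patient whose last chemotherapy was 31 days before registration meets 3.26. A baseline scan 28 days before registration then falls 31−28 = 3 days after that dose. Four cycles are 4×28 = 112 days, and treatment starts 0 to 7 days after registration. Success through SD therefore needs control lasting 31+0+112 = 143 to 31+7+112 = 150 days after the last chemotherapy. For an agent stopped the day before registration, the span is 1+0+112 = 113 to 1+7+112 = 120 days. No calculation above addresses how often the washout gap would be used; the documents give no basis for one.

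**The case against.** The strongest reply is that admitting intolerant patients is deliberate and contradicts no other criterion. In a molecularly selected disease, requiring progression could cost accrual: f=30% would be about 8 of 27 patients (0.3×27 = 8.1). That stands, and mandatory progression is not proposed.

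A reader might infer that residual effect of earlier therapy will be scored as ponatinib benefit. The documents do not show this. Residual chemotherapy effect alone would have to last 143 to 150 days. The early baseline also works in both directions: late shrinkage could help a PR measured from baseline, but a scan taken while disease is still controlled sets a low reference, so regrowth meets the PD rule in 11.432 sooner. Stable or indolent disease at entry is the better-supported route.

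A reader might also infer that 3.26 covers nothing but chemotherapy, or that patients found by sequencing will often come straight from another FGFR-matched drug. Section 3.26 also names radiation therapy and major surgery, and 3.29c arguably excludes prior similar kinase inhibitors altogether. The gap concerns the remaining non-chemotherapy agents, and how often it would arise is unknown.

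Two further points stand. The 5% comes from response rates while the endpoint also counts SD, so 5% may be too low even for refractory patients; that is a separate and possibly larger issue, and the rise above 0.12 cannot all be assigned to eligibility. And 3 of 27 does not bind the sponsor: 16.212 says further testing may be recommended, and 16.25 brings quality and duration of response into a decision to terminate. These considerations soften the consequence, but they do not identify the patients concerned.

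**Conclusion.** The point holds in limited form. Non-progressing patients are eligible, their status is not among the recorded factors, and lasting SD in them counts in full against a null drawn from refractory tumors. Chemotherapy is the only systemic drug therapy with a stated washout.

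The size is conditional. With an inactive drug, P(go) runs from 0.12 (s no higher than the null) through 0.148 at f=10%, s=10%, still within the plan's limit, to 0.58 at f=30%, s=30%. A reader might take the upper figures as the trial's actual error rate. The documents do not support that, because f, s and the 5% for refractory patients are all assumed. What can be said firmly is that the margin is thin: a pooled background rate just above 5.5% takes the false-positive probability past 0.15.

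This is a low-cost improvement in wording and reporting. It does not invalidate the design.

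**What to change.** 1. In 3.26, replace the reference to systemic chemotherapy with *systemic anticancer therapy of any kind*. Keep the protocol's own 30-day window and leave 3.28 unchanged.
2. Leave 3.13 as it is. Add to Section 12: *Documented progression on or after last prior therapy: Yes vs No*, completed at registration.
3. Add to 16.312 a prespecified supporting clinical benefit rate, reported beside the primary rate. It credits SD for 4 or more cycles only to patients with documented progression at entry; all others count as successes only on confirmed CR or PR. The denominator remains all evaluable patients.

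The primary rate, the two-stage rule, the sample size and the table in 16.24 are unchanged. The cost is a short delay for a few patients coming off non-chemotherapy agents, one extra field at registration, and a supporting rate that may look slightly less favorable than the primary one.
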